1.5.5 Benefit-Risk Assessment

In summary, this study combines treatments with different mechanisms of action that have demonstrated clinical activity against B-cell lymphoma. Currently available data for obinutuzumab or rituximab in combination with either atezolizumab or polatuzumab vedotin support and provide the rationale for a potentially improved benefit-risk ratio in patients with FL or DLBCL and further support the clinical development of the triple combination. Overlapping toxicities are anticipated and will be closely monitored and managed in the clinical trial setting with adverse event management guidance and periodic safety data review. Additionally, drug-drug interactions (DDIs) are unlikely to occur (see Section 5.1.5).

Following the Dear Investigator Letter issued on 1 March 2018 due to a safety signal observed in the G+Atezo+Pola treatment group (see Section 1.5.1 and Section 5.1.6) and evaluation of preliminary safety and efficacy data from the two study treatment groups, the Sponsor assesses the benefit-risk of atezolizumab + obinutuzumab + polatuzumab vedotin in patients with RR FL and of atezolizumab + rituximab + polatuzumab vedotin in patients with RR DLBCL to be un compelling (see Section 1.5.1). Due to the perceived role of atezolizumab in the T-cell mediated events, the Sponsor decided to discontinue atezolizumab in all patients still receiving study treatment, but allow patients deriving benefit to continue study treatment without atezolizumab. The benefit-risk of obinutuzumab + polatuzumab vedotin and rituximab + polatuzumab vedotin combinations, without atezolizumab, remains unchanged, with no new safety signals derived from ongoing studies (see Section 1.5.4.3 and the Polatuzumab Investigator's Brochure).

2. OBJECTIVES AND ENDPOINTS

This study will evaluate the safety, efficacy, pharmacokinetics, and immunogenicity of induction treatment consisting of obinutuzumab in combination with atezolizumab plus polatuzumab vedotin (G+Atezo+Pola) in patients with relapsed or refractory FL and rituximab in combination with atezolizumab + polatuzumab vedotin (R+Atezo+Pola) in patients with relapsed or refractory DLBCL, followed by post-induction treatment with G+Atezo (referred to as maintenance) in patients with FL who achieve a CR, a PR, or stable disease at EOI and post-induction treatment with R+Atezo (referred to as consolidation) in patients with DLBCL who achieve a CR or PR at EOI (see Section 3.1 for details). Specific objectives and corresponding endpoints for the study are outlined below, in accordance to study changes from Protocol BO29561, Version 7.

In this study, "study treatment" refers to the combination of all study treatment components.

2.1 SAFETY OBJECTIVE

The safety objectives for this study are as follows:

- To determine the recommended Phase II dose (RP2D) for polatuzumab vedotin when given in combination with fixed doses of obinutuzumab and atezolizumab on the basis of the following endpoint:

Incidence of DLTs during Cycles 1 and 2 of study treatment:

- To evaluate the safety and tolerability of the G+Atezo+Pola treatment group and the R+Atezo+Pola treatment group on the basis of the following endpoints:
 - Nature, frequency, severity, and timing of adverse events
 - Changes in clinical laboratory results during and following study treatment administration

2.2 EFFICACY OBJECTIVES

Response will be determined through use of the PET-CT scans or CT scans alone, using Revised Lugano Response Criteria for Malignant Lymphoma (Cheson et al. 2014; see [Appendix 5](#)), hereinafter referred to as modified Lugano 2014 criteria. Response will be determined by the investigator.

2.2.1 Primary Efficacy Objective

The primary efficacy objective for this study is to evaluate the efficacy of induction treatment with G+Atezo+Pola in relapsed or refractory FL and R+Atezo+Pola in relapsed or refractory DLBCL on the basis of the following endpoint:

- CR at EOI, as determined by the investigator on the basis of PET-CT scans

2.2.2 Secondary Efficacy Objectives

The secondary efficacy objective for this study is to evaluate the efficacy of induction treatment with G+Atezo+Pola and maintenance treatment with G+Atezo in relapsed or refractory FL and of induction treatment with R+Atezo+Pola and consolidation treatment with R+Atezo in relapsed or refractory DLBCL on the basis of the following endpoints:

- CR at EOI, as determined by the investigator on the basis of CT scans alone
- Objective response (defined as a CR or PR) at EOI, as determined by the investigator on the basis of PET-CT scans
- Objective response (defined as a CR or PR) at EOI, as determined by the investigator on the basis of CT scans alone
- Best response of CR or PR during the study, as determined by the investigator on the basis of CT scans alone

2.2.3 Exploratory Efficacy Objectives

The exploratory efficacy objective for this study is to evaluate the long-term efficacy of G+Atezo+Pola on the basis of the following endpoints:

- For patients who have positive PET scans at EOI:
CR at 12 months, as determined by the investigator on the basis of PET-CT scans in FL patients
- Overall survival (OS), defined as the time from initiation of study treatment to death from any cause

2.3 PHARMACOKINETIC OBJECTIVE

The PK objective for this study is to characterize the pharmacokinetics of obinutuzumab, rituximab, atezolizumab, and polatuzumab vedotin when given in combination, on the basis of the following endpoints:

- Observed serum obinutuzumab concentration at specified timepoints
- Observed serum rituximab concentration at specified timepoints
- Observed serum atezolizumab concentration at specified timepoints
- Observed serum and plasma concentrations of polatuzumab vedotin and relevant analytes (total antibody, acMMAE, and unconjugated MMAE) at specified timepoints

2.4 IMMUNOGENICITY OBJECTIVES

The immunogenicity objective for this study is to evaluate the immune response to obinutuzumab, rituximab, atezolizumab, and polatuzumab vedotin on the basis of the following endpoints:

- Incidence of human anti-human antibodies (HAHAs) to obinutuzumab during the study relative to the prevalence of HAHAs at baseline
- Incidence of human anti-chimeric antibodies (HACAs) to rituximab during the study relative to the prevalence of HACAs at baseline
- Incidence of ATAs to atezolizumab during the study relative to the prevalence of ATAs at baseline
- Incidence of ATAs to polatuzumab vedotin during the study relative to the prevalence of ATAs at baseline

The exploratory immunogenicity objective for this study is to evaluate potential effects of HAHAs, HACAs or ATAs on the basis of the following endpoint:

- Correlation between HAHA, HACA or ATA status and efficacy, safety, or PK endpoints

2.5 BIOMARKER OBJECTIVE

The exploratory biomarker objective for this study is to identify non-inherited biomarkers that are predictive of response to study treatment (i.e., predictive biomarkers), are associated with progression to a more severe disease state (i.e., prognostic biomarkers),

are associated with acquired resistance to study treatment, are associated with susceptibility to developing adverse events, can provide evidence of study treatment activity, can increase the knowledge and understanding of lymphoma biology or study treatment mechanism of action, or can contribute to improvement of diagnostic assays, on the basis of the following endpoint:

- Association between non-inherited biomarkers (listed in Section [4.5.7](#)) and efficacy, safety, pharmacokinetic, or immunogenicity endpoints

3. STUDY DESIGN

3.1 DESCRIPTION OF THE STUDY

3.1.1 Overview of Study

This Phase Ib/II, open-label, multicenter, non-randomized, dose-escalation study will evaluate the safety, efficacy, pharmacokinetics, and immunogenicity of G + Atezo + Pola in patients with RR FL and R + Atezo + Pola in patients with RR DLBCL.

Following the Dear Investigator Letter issued on 1 March 2018, enrollment has been stopped and atezolizumab treatment has been discontinued in all patients still receiving study treatment. Protocol BO29561, Version 7 formalizes these changes to the study.

A study schema is provided in [Figure 1](#).

Overall, it was planned to have 83–92 patients enrolled in this study, at approximately 20 investigative sites around the world. As of 1 March 2018, 13 patients with RR FL and 23 patients with RR DLBCL were enrolled in the study.

To characterize the PK properties of obinutuzumab, rituximab, atezolizumab, and polatuzumab vedotin as well as the immunogenicity of obinutuzumab, rituximab, atezolizumab, and polatuzumab vedotin when given in combination, blood samples will be taken at various timepoints before and during dosing ([Appendix 2](#)).

During induction treatment, all patients will have a CT scan performed at the end of Cycle 2, to confirm absence of early disease progression. Because of the potential for tumor flares with immunotherapies, which result in early apparent radiographic progression (pseudoprogression/tumor immune infiltration), including the appearance of new lesions followed by delayed response (Wolchok et al. 2009), patients whose CT scans meet criteria for disease progression at the end of Cycle 2 may continue to receive study treatment, at the discretion of the investigator and following discussion with the Medical Monitor, if at least two of the following criteria are met:

- Absence of symptoms and signs that indicate unequivocal disease progression
- No decline in Eastern Cooperative Oncology Group (ECOG) Performance Status
- Absence of tumor progression at critical anatomical sites (e.g., leptomeningeal disease) that cannot be managed by protocol-allowed medical interventions

- Patients with radiographic evidence of progression at the end of Cycle 2 who continue to receive study treatment per the above criteria should have a CT scan repeated 4–8 weeks later.

3.1.2 G+Atezo+Pola Treatment Group (Patients with Follicular Lymphoma)

3.1.2.1 Dose-Escalation Phase

The purpose of the dose-escalation phase was to identify the RP2D for polatuzumab vedotin when combined with fixed doses of obinutuzumab and atezolizumab as induction treatment. A total of 9 patients with RR FL were enrolled in the dose-escalation phase (3 patients in the Pola 1.4-mg dose cohort and 6 patients in the Pola 1.8-mg dose cohort) and treated in accordance with the treatment regimens and the dose-escalation rules described in Section [3.1.2.1.2](#).

No DLTs were observed at either the Pola 1.4-mg or 1.8-mg Pola dose levels. Therefore, Pola 1.8 mg was selected as the RP2D, and enrollment in the expansion phase of the study proceeded.

3.1.2.1.1 Definition of Dose-Limiting Toxicity

In this study, a DLT is defined as any one of the following events occurring during Cycles 1 and 2 of treatment and assessed by the investigator as related to study treatment:

- Adverse event of any grade that leads to a delay of more than 14 days the start of the next treatment cycle
- Hematologic adverse event that meets any of the following criteria:
 - Grade 3 or 4 neutropenia in the presence of sustained fever of $>38^{\circ}\text{C}$ (lasting >5 days) or a documented infection
 - Grade 4 neutropenia lasting >7 days
 - Grade 3 or 4 thrombocytopenia that results in significant bleeding per investigator judgment
 - Grade 4 thrombocytopenia lasting >7 days
- Grade 3 or 4 non-hematologic adverse event, with the following exceptions:
 - Grade 3 or 4 IRRs
 - Note that IRRs may occur even after a small amount of drug has been administered (i.e., IRRs are not dose dependent).
 - Grade 3 diarrhea that responds to therapy within 72 hours
 - Grade 3 nausea or vomiting that occurs in the absence of premedication and responds to adequate therapy within 72 hours
 - Grade 3 fatigue that resolves to Grade ≤ 2 within 7 days
 - Grade 3 laboratory abnormality that is asymptomatic and deemed by the investigator not to be clinically significant

Other toxicities occurring during Cycles 1 and 2 that are considered to be clinically relevant and related to study treatment, as determined by the investigator and the Medical Monitor may also be considered DLTs.

3.1.2.1.2 Treatment Regimens and Dose-Escalation Rules

A 3+3 dose-escalation schema was used. Induction treatment was administered in 21-day cycles, as outlined in [Table 1](#). Obinutuzumab and atezolizumab will remain at fixed doses during the dose-escalation phase. For polatuzumab vedotin, there are two possible dose levels: 1.4 or 1.8 mg/kg. If the starting dose of 1.4 mg/kg is safe and tolerable, the polatuzumab vedotin dose will be escalated to 1.8 mg/kg. Intrapatient dose escalation is not allowed.

Table 1 Induction Treatment for Dose-Escalation Phase

Cycle	G + Atezo + Pola (21-Day Cycles)
1	Obinutuzumab 1000 mg IV on Days 1, 8, and 15 Polatuzumab vedotin 1.4 mg/kg or 1.8 mg/kg IV on Day 1
2–6	Obinutuzumab 1000 mg IV on Day 1 Atezolizumab 1200 mg IV on Day 1 Polatuzumab vedotin 1.4 mg/kg or 1.8 mg/kg IV on Day 1

IV=intravenous.

Dose escalation occurred in accordance with the rules listed below:

First Dosing Group (Polatuzumab Vedotin 1.4 mg/kg)

- A minimum of 3 patients will initially be sequentially enrolled in the first dosing group (polatuzumab vedotin 1.4 mg/kg). The 3 patients will be enrolled at least 24 hours apart.
- If none of the first 3 DLT-evaluable patients experiences a DLT, enrollment of the second dosing group (i.e., polatuzumab vedotin 1.8 mg/kg) may proceed.
- If 1 of the first 3 DLT-evaluable patients experiences a DLT, the dosing group will be expanded to at least 6 patients. If there are no further DLTs in the first 6 DLT-evaluable patients, enrollment of the second dosing group may proceed.
- If 2 or more of the first 3–6 DLT-evaluable patients experience a DLT, the RP2D will have been exceeded, and dose escalation will stop and study will be discontinued.

Second Dosing Group (Polatuzumab Vedotin 1.8 mg/kg)

- A minimum of 3 patients will initially be enrolled sequentially in the second dosing group (polatuzumab vedotin 1.8 mg/kg). The 3 patients will be enrolled at least 24 hours apart.
- If none or 1 of the first 3 DLT-evaluable patients experiences a DLT, the dosing group will be expanded to at least 6 patients. If there are no further DLTs, 1.8 mg/kg will be declared the RP2D for polatuzumab vedotin.

- If 2 or more of the first 3–6 DLT-evaluable patients experience a DLT, the RP2D will have been exceeded, and 1.4 mg/kg will be declared the RP2D for polatuzumab vedotin.

The highest dose at which fewer than 2 of 6 patients DLT-evaluable patients (i.e., <33%) experience a DLT was declared the RP2D for polatuzumab vedotin that will be used in the expansion phase.

On the basis of a review of real-time safety data and available preliminary PK data, dose escalation may be halted or modified by the Sponsor as deemed appropriate.

Relevant demographic, adverse event, laboratory, and PK (if available) data will be reviewed prior to dose-escalation decisions, by the Medical Monitor in consultation with the Principal Investigator and participating investigators.

Although the DLT assessment window is defined as Cycles 1 and 2, cumulative toxicities occurring beyond Cycle 2 may be considered when determining the RP2D.

Patients enrolled in the dose-escalation phase that achieved a CR, a PR, or stable disease at EOI received maintenance treatment with G+Atezo.

As of 1 March 2018, patients with RR FL eligible to or already receiving maintenance treatment will continue to receive obinutuzumab maintenance treatment, as outlined in [Table 2](#). Maintenance treatment should start 8 weeks (\pm 1 week) after Day 1 of Cycle 6 and will continue until disease progression or unacceptable toxicity for up to 24 months.

Table 2 Maintenance Treatment for the G+Atezo+ Pola Treatment Group

Patients	Treatment
Patients with FL	Maintenance treatment consisting of the following, administered for 24 months ^a (from Month 1–Month 24): Obinutuzumab 1000 mg IV on Day 1 of every other month (i.e., every 2 months), starting with Month 1

FL=follicular lymphoma; IV=intravenous.

^a 1 month=28 days.

3.1.2.2 Expansion Phase

The expansion phase was designed to further assess the safety and efficacy of the combination of atezolizumab with obinutuzumab plus polatuzumab vedotin, when given as induction treatment and atezolizumab with obinutuzumab as maintenance treatment in patients with FL.

During the expansion phase, 34–37 patients with FL (for a total of 40 patients with FL treated at the RP2D in the dose-escalation and expansion phases) were planned to be enrolled. As of 1 March 2018, patients with RR FL will continue to be treated as outlined in [Table 3](#).

Table 3 Induction Treatment for Expansion Phase

Cycle	G + Atezo + Pola (21-Day Cycles) Treatment Group
1–6	Obinutuzumab 1000 mg IV on Days 1, 8, and 15 Polatuzumab vedotin at 1.8 mg/kg IV on Day 1

IV=intravenous.

Patients with FL who achieve a CR, a PR, or stable disease at EOI will receive maintenance treatment with obinutuzumab, as outlined in [Table 2](#). Maintenance treatment should start 8 weeks (\pm 1 week) after Day 1 of Cycle 6 and will continue until disease progression or unacceptable toxicity for up to 24 months. Polatuzumab vedotin will not be given as a post-induction treatment.

3.1.3 R + Atezo + Pola Treatment Group (Patients with Diffuse Large B-Cell Lymphoma)

Study enrollment took place in two phases: an initial safety run-in phase followed by an expansion phase.

A total of 7 patients with RR DLBCL were enrolled into the safety run-in phase at the Pola 1.8-mg dose level, and treated in accordance with the treatment regimens and the dose-escalation rules described in Section [3.1.3.1](#). No DLTs were observed, and Pola 1.8 mg was selected as the RP2D, and enrollment in the expansion phase of the study proceeded.

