3.3.2 Rationale for Dose and Schedule

3.3.2.1 Rationale for Obinutuzumab and Rituximab Dose and Schedule

For patients with FL, the dose and schedule of obinutuzumab in the induction regimen will be 1000 mg IV on Days 1, 8, and 15 of Cycle 1 and Day 1 of each subsequent 21-day cycle (Cycles 2–6). This is based on the recommended dose and schedule of obinutuzumab in the ongoing Phase III program in patients with NHL. For this protocol, patients will be treated for 6 cycles during the induction phase. The dose and schedule of obinutuzumab in the maintenance regimen (FL) will be 1000 mg IV administered every 2 months for up to 2 years. This dosing administration is based on the obinutuzumab maintenance regimen that was administered in the Phase III GAO4753g study (Sehn et al. 2015).

For patients with DLBCL, the dose and schedule of rituximab in the induction regimen will be 375 mg/m² on Day 1 of each 21-day cycle (Cycles 1–6). This is based on the recommended dose and schedule for rituximab in this setting (see Rituximab Investigator's Brochure and NCCN Guidelines® 2016). For this protocol, patients will be treated for 6 cycles during the induction phase. The dose and schedule of rituximab in the consolidation regimen (DLBCL) was 375 mg/m² IV administered every 2 months for up to 8 months. The consolidation regimen was modeled after the FL maintenance therapy. The rationale for treatment duration is presented in Section 3.3.2.4.

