4.2 METHOD OF TREATMENT ASSIGNMENT

This is a Phase Ib/II, open-label, multicenter, non-randomized, dose-escalation study of G+Atezo+Pola in patients with relapsed or refractory FL and R+Atezo+Pola in patients with relapsed or refractory DLBCL. During the dose-escalation phase, an interactive voice or web-based response system (IxRS) was used to assign patients with relapsed or refractory FL to dosing groups that vary according to the dose of polatuzumab vedotin given during induction treatment. During the expansion phase, patients with relapsed or refractory FL and DLBCL will receive polatuzumab vedotin at the RP2D during induction treatment. Atezolizumab and obinutuzumab or rituximab was to be given at stable doses to all patients, during both induction and post-induction treatment. Post-induction treatment (for eligible patients only) will depend on lymphoma histology (see Section 3.1 for details). As of 1 March 2018, patients with RR FL in the expansion phase will continue to be treated with G+Pola during induction (see [Table 3](#)) and patients on maintenance treatment will continue treatment with obinutuzumab (see [Table 2](#)). Patients with RR DLBCL will continue to be treated with R+Pola during induction (see [Table 4](#)), and patients with RR DLBCL who have completed or prematurely discontinued induction treatment will proceed to the safety follow-up without consolidation treatment.

Enrollment tracking will be performed through use of the IxRS. Prior to initiation of screening, the study site should confirm via the IxRS that slots are available for enrollment. After written informed consent has been obtained and preliminary eligibility has been established, the study site will submit documentation supporting eligibility to the Sponsor and obtain the Sponsor's approval to enroll the patient. Once the Sponsor

reviews and approves the patient for enrollment, the patient number will be assigned and the patient will be enrolled via the IxRS. The Sponsor will communicate to the sites impending closure of screening for the dose-escalation and expansion phases.

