4.3.2 Dosage, Administration, and Compliance

The treatment regimens are summarized in [Table 6](#), [Table 7](#), and [Table 8](#) (see Sections [4.3.2.4](#) and [4.3.2.5](#)). Premedication should be administered as described in Section [4.3.2.7](#).

Any overdose or incorrect administration of any of the study treatments should be noted on the Study Drug Administration electronic Case Report Form (eCRF). Adverse events associated with an overdose or incorrect administration of any of the study treatments should be recorded on the Adverse Event eCRF.

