4.3.2.1 Obinutuzumab

[figure not shown]
Obinutuzumab will be administered by IV infusion at an absolute (flat) dose of 1000 mg on Days 1, 8, and 15 of the first cycle and on Day 1 of each subsequent cycle during induction treatment, and on Day 1 of every other month (i.e., every 2 months) during maintenance treatment.

Obinutuzumab should be administered as an IV infusion through a dedicated line in an environment in which full resuscitation facilities are immediately available and under the close supervision of an experienced physician. Obinutuzumab infusions will be administered per the instructions outlined in [Figure 2](#) and [Figure 3](#). For patients with bulky lymphadenopathy, the infusion may be given slowly over a longer period of time, or the dose may be split and given over more than 1 day.

No dose modification for obinutuzumab is allowed. Additional guidelines for treatment delays or discontinuation are provided in Section [5.1.6](#).

Premedication with a corticosteroid, antihistamine, and analgesic/antipyretic, as outlined in Section [4.3.2.7](#) and [Table 9](#), is required to reduce the incidence and severity of IRRs. For anaphylaxis precautions, see [Appendix 9](#).

Figure 2 Guidelines for Obinutuzumab Infusions: First Infusion

[figure not shown]

IRR=infusion-related reaction.

^a All patients should receive full premedication with oral corticosteroid, oral analgesic/anti-pyretic, and antihistamine prior to the first obinutuzumab infusion. Refer to Section 4.3.2.7 for details.

^b Supportive treatment should include acetaminophen/paracetamol and an antihistamine such as diphenhydramine, if not administered within the previous 4 hours. Intravenous saline may be indicated. For bronchospasm, urticaria, or dyspnea, patients may require antihistamines, oxygen, corticosteroids (e.g., 100 mg oral prednisone or equivalent), and/or bronchodilators. For anaphylaxis precautions, see Appendix 9.

Figure 3 Guidelines for Obinutuzumab Infusions: Second and Subsequent Infusions

IRR = infusion-related reaction.

- ^a Patients should receive full premedication with oral corticosteroid, antihistamine, and oral analgesic/anti-pyretic prior to the obinutuzumab infusion. Refer to Section 4.3.2.7 for details. In the case of a recurrent Grade 3 IRR, obinutuzumab may be discontinued at the discretion of the investigator, following an individual benefit-risk assessment.

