First Infusion (Day 1 of Cycle 1)	Subsequent Infusions

Begin infusion at an initial rate of 50 mg/hr.If no infusion-related or hypersensitivity reaction occurs, increase the infusion rate in 50-mg/hr increments every 30 minutes to a maximum of 400 mg/hr.If a reaction develops, stop or slow the infusion. Administer medications and supportive care in accordance with institutional guidelines. If the reaction has resolved, resume the infusion at a 50% reduction in rate (i.e., 50% of rate being used at the time when the reaction occurred).	
If the patient experienced an infusion-related or hypersensitivity reaction during the prior infusion, use full premedication, including 100 mg of prednisone/prednisolone or 80 mg of methylprednisolone or equivalent (until no further IRR occurs); begin infusion at an initial rate of 50 mg/hr; and follow instructions for first infusion.If the patient tolerated the prior infusion well (defined by an absence of Grade 2 reactions during a final infusion rate of \geq 100 mg/hr), begin infusion at a rate of 100 mg/hr.If no reaction occurs, increase the infusion rate in 100-mg/hr increments every 30 minutes to a maximum of 400 mg/hr.If a reaction develops, stop or slow the infusion. Administer medications and supportive care in accordance with institutional guidelines. If the reaction has resolved, resume the infusion at a 50% reduction in rate (i.e., 50% of rate being used at the time when the reaction occurred).

No dose modification for rituximab is allowed. Guidelines for treatment delays or discontinuation are provided in Section 5.1.6.

Premedication with a corticosteroid, analgesic/antipyretic, and antihistamine, as outlined in Section 4.3.2.7, is required to reduce the incidence and severity of IRRs. For anaphylaxis precautions, see Appendix 9.

4.3.2.5 Induction Treatment with Obinutuzumab or Rituximab, and Polatuzumab Vedotin (G+Pola or R+Pola)

Patients will receive induction treatment, administered in 21-day cycles, as follows:

- Patients with FL will receive 6 cycles of induction treatment consisting of obinutuzumab and polatuzumab vedotin for Cycles 1–6 as outlined in Table 6.
- Patients with DLBCL will receive 6 cycles of induction treatment consisting of rituximab and polatuzumab vedotin for Cycles 1–6 as outlined in Table 7.

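### Table 3 lists obinutuzumab on Days 1, 8 and 15 in all six induction cycles (18 doses); the rest of the protocol gives 8 doses

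*Combined protocol and SAP*

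**What the plan says.** Section 3.1.2.2 introduces Table 3 with "As of 1 March 2018, patients with RR FL will continue to be treated as outlined in" and then cites the table. Table 3 has one row, for Cycles 1–6: "Obinutuzumab 1000 mg IV on Days 1, 8, and 15 Polatuzumab vedotin at 1.8 mg/kg IV on Day 1". Section 4.2 cites Table 3 again, saying that "patients with RR FL in the expansion phase will continue to be treated with G+Pola during induction".

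The full schedule is set out in five other places:

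- **Table 1 (Section 3.1.2.1.2, dose escalation).** A Cycle 1 row has Days 1, 8 and 15. A separate Cycles 2–6 row begins "Obinutuzumab 1000 mg IV on Day 1 Atezolizumab 1200 mg IV on Day 1".
- **Section 3.3.2.1 (dose rationale).** "1000 mg IV on Days 1, 8, and 15 of Cycle 1 and Day 1 of each subsequent 21-day cycle".
- **Section 4.3.2.1 (dosing).** "on Days 1, 8, and 15 of the first cycle and on Day 1 of each subsequent cycle during induction treatment".
- **Table 6 (FL induction).** Days 1, 8 and 15 in the Cycle 1 column; Day 1 in the Cycles 2–6 column. Section 4.3.2.5 directs FL patients here: "Patients with FL will receive 6 cycles of induction treatment consisting of obinutuzumab and polatuzumab vedotin for Cycles 1–6 as outlined in Table 6".
- **Appendix 1.** The obinutuzumab administration row has three Cycle 1 visits and a single Day 1 column for Cycles 2–6.

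**The concern.** The protocol carries two obinutuzumab induction schedules for the same patients, and the one in the table titled for the expansion phase differs from all the rest. Followed literally, Table 3 adds two 1000 mg infusions to each of Cycles 2–6, with no rationale anywhere in the protocol. The stated regimen change was the removal of atezolizumab, with the other drugs continuing (Section 1.5.4).

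There is also a secondary reporting question. Section 6.3 promises summaries of doses received and relative dose intensity and a listing of major protocol violations, without naming the table that defines the planned dose. If Table 3 were used, correctly treated patients would appear under-dosed.

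**Working it through.** **1. Dose counts over a full induction course (six cycles, 1000 mg per dose)**

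| Source | Cycle 1 | Cycles 2–6 | Doses | Total |
|---|---|---|---|---|
| Table 3 as printed | 3 | 5 × 3 = 15 | 18 | 18,000 mg |
| Table 1, 3.3.2.1, 4.3.2.1, Table 6, Appendix 1 | 3 | 5 × 1 = 5 | 8 | 8,000 mg |

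The difference is 10 doses, and 18/8 = 2.25. The protocol prints the schedules, not these totals.

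**2. Which entry is wrong**

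Three other rules fit the 8-dose schedule, although none states it in full:

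- Table 9 has premedication rows for Cycle 1 Days 8 and 15, and only Day 1 from Cycle 2 onward.
- Section 5.1.7.2 and Table 13 treat Days 8 and 15 of Cycle 1 as the obinutuzumab-only visits.
- The general delay rule in Table 14 mentions Days 8 and 15 for Cycle 1 only.

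The extra infusions in Table 3 therefore have no premedication row and no administration visit. Table 3's obinutuzumab wording is that of the Cycle 1 row in Table 1, applied to all six cycles. A likely cause is that two rows were merged when atezolizumab was removed; that is inference.

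The hematology entries for Cycle 2 Days 8 and 15 in Appendix 1 do not support Table 3. The same entries appear in the DLBCL schedule (Appendix 2), where no drug is given on those days.

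**3. Size of the gap from 1 March 2018**

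Let k be the number of Cycles 2–6 a patient still had to receive on that date. The documents do not give k, so the range is 0 to 5. Cycle 1 is the same under both schedules.

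- Planned doses if Table 3 governs the remaining cycles: 3 + (5 − k) + 3k = 8 + 2k
- Excess over the intended 8: 2k

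Section 6.1 reports 13 FL patients enrolled, 9 of them in dose escalation, so at most 13 − 9 = 4 were in the expansion phase. The largest total excess is 4 × 2k = 8k.

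**4. Conditional effect on relative dose intensity**

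Section 6.3 gives no formula. Assume total dose received over total dose planned, a patient who received all 8 intended doses, and an analyst who takes the plan from Table 3. The ratio is then 8/(8 + 2k).

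| k | Excess doses per patient | Excess, 4 patients | 8/(8 + 2k) |
|---|---|---|---|
| 0 | 0 | 0 | 100% |
| 1 | 2 | 8 | 80% |
| 2 | 4 | 16 | 67% |
| 3 | 6 | 24 | 57% |
| 4 | 8 | 32 | 50% |
| 5 | 10 | 40 | 44% |

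**The case against.** The strongest reply is that this is a clerical slip in text no longer in use. Enrollment has stopped (Section 3.1.1), and Section 3.1.4 says patients no longer receive polatuzumab vedotin, so no one appears able to be dosed from an induction table under Version 8. The operative dosing text is also right. Section 4.3.2 says "The treatment regimens are summarized in" Tables 6, 7 and 8 and does not name Table 3, and the Appendix 1 footnote on dosing sends sites to Sections 4.3.2 and 4.3.2.5.

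The dose-intensity figures are open to challenge too. They require an analyst to pass over every correct statement of the schedule, they rest on an assumed formula, and k = 0 is as compatible with the documents as k = 5. Table 1 covers a different phase, so it is not a competing schedule for the expansion patients.

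Most of this stands, and it limits the consequence. It does not remove the error: Table 3 is current text, cited twice as the schedule for these patients, and it contradicts Section 3.3.2.1, Section 4.3.2.1, Table 6 and Appendix 1, which apply to FL patients generally. A text-extraction fault is unlikely, because the row reads complete and Table 4 uses the same one-row layout (correctly, since rituximab is given on Day 1 only). The page image was not available to exclude it.

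**Conclusion.** The concern holds. Table 3 states a wrong dosing rule: 18 induction doses where 8 are intended. It should be corrected, but the reach is small. From 1 March 2018 the excess would be 0 to 10 doses per patient and 0 to 40 in total. The total assumes that Table 3 covers expansion patients only, as its title and Section 4.2 indicate. The upper end needs all four to have had Cycles 2–6 entirely ahead of them.

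Nothing in the documents shows that anyone was dosed from Table 3. The primary analysis in Section 6.6.1, the proportion in complete response at end of induction, does not use planned dose and is unaffected. The fall in relative dose intensity, to 44% at worst, would occur only if Table 3 were taken as the planned dose in the Section 6.3 summaries.

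**What to change.** At the next revision, split Table 3 into two rows that match Table 6:

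- **Cycle 1:** obinutuzumab 1000 mg IV on Days 1, 8 and 15; polatuzumab vedotin 1.8 mg/kg IV on Day 1.
- **Cycles 2–6:** obinutuzumab 1000 mg IV on Day 1; polatuzumab vedotin 1.8 mg/kg IV on Day 1.

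The 8-dose schedule (8,000 mg) is then the only induction reference for exposure and deviation summaries. Section 6.3 needs no change and no separate record check is needed: Sections 4.3.2, 6.3 and 9.2 already provide for recording incorrect administration, listing dosing data and documenting deviations. The cost is one table row split into two, with no new data and no change to any analysis or any patient's treatment.
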